# 10.5.1 Screening Period

Visit SCR (day -8 to 0)		
Administrative & regulatory		Written informed consent
	•	Assign participant screening number
Clinical	• • •	Demographic data: Date of birth, ethnic group, sex Medical history, incl. treatment history and current concomitant medication Physical examination, Vital signs (temperature, blood pressure, pulse, pulse oxymetry and respiratory rate) after 10 mins supine rest Weight (kg)/height (m) Neurological examination, vision testing
Laboratory	Blood • • •	Serum pregnancy test (blood sample of 7.5mL), if female of childbearing potential HIV test and CD4 count (blood sample of 7.5mL) Host biomarker and pharmacogenomics blood sample, if consent for this sub study is given Screening laboratory (blood sample of 12.5mL)
	Urine •	Urine drug screening Urinalysis
Microbiology	•	Spontaneously produced sputum Ziehl-Neelsen smear from concentrated sample Susceptibility testing for RIF and INH by rapid test
Other	•	Inclusion and exclusion criteria Chest X-ray (if no chest X-ray is available no older than 2 weeks) ECG (12 lead, single) after 10 mins supine rest
Study drugs	•	N/A

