# 10.5.2 Treatment Period

Visits WK 00 – WK 16 (Day 01 – Day	11	2, each ±2 days with exception of day 14 (-2 days window))
Administrative & regulatory	•	Randomization (before/at WK00 only)

Protocol No: PanACEA - DECODE – 01/ LCB01-0371-20-2-02 Protocol Version No: V2.1, dated 08 September 2021

		
 
Enrolment (WK00 only)
 
Hospitalization* (WK 02 only)
 

Clinical (before intake o	of IMP)	
 
Physical examination, vital signs, weight Additional blood pressure and heart rate measurements at WK00: 1h, 2h and 3h (± 10 mins) after intake of IMP, at WK02 during hospitalization: 1h, 2h, 3h, 4h, 6h (± 10 ins) after intake of IMP with a meal
 
Neurological examination/vision testing (not WK 00)
 
Concomitant medication
 
Adverse events
 
Hospitalization: WK02 visit only, for intensive PK sampling after dosing together with standardized meal.
 

Laboratory Blo (before intake of IMP)	Blood	
 
Safety Lab (WK01-09, WK11, WK13, WK16): haematology and biochemistry (blood sample of 9.5mL), Coagulation only at WK 02 and if clinically indicated (additional blood sample of 3mL); to be sampled before study treatment administration
 
Serum pregnancy test (blood sample of 7.5mL), if female of childbearing potential (WK09 only)
 
Host biomarker blood sampling only at WK02, WK04, WK07, WK11, WK13 and WK16, if consent for this sub study is given
 
Intensive PK sampling DZD (WK02 only): 0 (within 1h before dosing), 1, 2, 4, 8, 12, (± 10 mins) and 24 hours (± 30 mins) after dosing
 

-	Urine	• Urinalysis (WK01-09, WK11, WK13, WK16): per dipstick, additional microscopy on abnormal dipstick results
Microbiology		
 
Sputum (3 samples per visit, one of which may be an early morning sample – to be specified in the microbiology laboratory manual)
 
AFB smear from screening and WK16 samples
 
Culture in BD MGIT liquid media from 2 spot sputum samples
 
Culture on LJ solid media from 2 samples (WK00, WK08, WK12 and WK16 only)
 
Susceptibility testing: minimum inhibitory concentration (MIC) for drugs the participant is receiving will be tested on a representative MTB isolate from baseline and from WK08 or later, if any growth detected
 
Storage of the 3rd sputum sample
 

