#### 20.1.2 Closer observation: AST/ALT > 3xULN

It is critical to initiate close observation immediately upon detection and confirmation of early signals of possible DILI, and not to wait until the next scheduled visit or monitoring interval.

A threshold of aminotransferase levels greater than 3xULN is recommended for closer observations, as lesser elevations are common and nonspecific, **if participant is asymptomatic regarding clinical signs of DILI AND bilirubin AND INR are not elevated.** 

Other laboratory findings that do not meet these criteria but raise the investigator's concern should be discussed with the sponsor medical expert.

If additional testing, beyond that specified in the trial protocol, is carried out, it is important that the subject's information be added to the CRFs and database.

Close observation includes:

- Repeating liver enzyme, serum bilirubin tests and coagulation tests two or three times weekly. Frequency of retesting can decrease to once a week or less if abnormalities stabilize or the trial drug has been discontinued and the subject is asymptomatic.
- Obtaining a more detailed history of symptoms and prior or concurrent diseases.

- Obtaining a history of concomitant drug use (including non-prescription medications and herbal and dietary supplement preparations), but especially alcohol use, recreational drug use, and special diets.
- Ruling out acute viral hepatitis types A, B, C, D, and E; hypoxic/ischemic hepatopathy as much as possible; and biliary tract disease. Ultrasound should be performed for the latter.
- Obtaining a history of exposure to environmental chemical agents.
- Obtaining additional tests to evaluate liver function, as appropriate (e.g., INR, direct bilirubin).

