12.6. Visit Windows

For timing of data items, the time is based on actual visit dates where data was collected (e.g. blood sample, sputum sample, data recorded) rather than scheduled visit name or date. The time from randomization is calculated as the difference between visit date and randomization date + 1 (so that data collected on the day of randomization is on day = 1).

Any visit, scheduled or unscheduled, that falls into the analysis window below will be assigned to that visit for the purpose of analysis. If two visits fall within the same interval, the one closet to the target date will be used for the analyses by visit, so that there is only one unique visit for each patient and analysis time-point. These visit windows relate to analyses of tabulations of data by visit.

Visit	Target Date: Days after Treatment	nt Analysis Window
	Allocation (wk*7+1)	
Baseline	1	Date of screening consent-3
Week 01	7	4-10
Week 02	14	11-17
Week 03	21	18-24
Week 04	28	25-31
Week 05	35	32-38
Week 06	42	39-45
Week 07	49	46-52
Week 08	56	53-59

Week 09	63	60-66
Week 10	70	67-73
Week 11	77	74-80
Week 12	84	81-87
Week 13	91	88-94
Week 14	98	95-101
Week 15	105	102-108
Week 16	112	109-121
Week 18	126	122-154
Week 26	182	155-210
Week 38	266	211-313
Week 52	364	314-no upper bound

13. Safety Analysis

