3.1 ECG

These tables will be produced for QTcF,QT, PR, RR, QRS.

OTcF

Table 3.1.1 Summary of QTcF by Treatment Arm

QTcF (Friderica's correction)	Arm 1 D0 (N=x) n (%)	Arm 2 D400 (N=x) n (%)	Arm 3 D800-OD (N=x) n (%)	Arm 4 D1200 (N=x) n (%)	Arm 5 D800-BD (N=x) n (%)	Total (N=x) n (%)
QTcF < 450 ms	xx (xx.x %)	xx (xx.x %)	xx (xx.x %)	xx (xx.x %)	xx (xx.x %)	xx (xx.x %)
450 ms ≤ QTcF <480 ms	xx (xx.x %)	xx (xx.x %)	xx (xx.x %)	xx (xx.x %)	xx (xx.x %)	xx (xx.x %)
480 ms ≤ QTcF < 500 ms	xx (xx.x %)	xx (xx.x %)	xx (xx.x %)	xx (xx.x %)	xx (xx.x %)	xx (xx.x %)
QTcF ≥ 500 ms	xx (xx.x %)	xx (xx.x %)	xx (xx.x %)	xx (xx.x %)	xx (xx.x %)	xx (xx.x %)

Table 3.1.2 Participants Proportion of QTcF Changes from Baseline by Treatment Arm

QTcF Changes	Arm 1	Arm 2	Arm 3	Arm 4	Arm 5	Total
from Baseline	D0	D400	D800-OD	D1200	D800-BD	(N=x)
	(N=x)	(N=x)	(N=x)	(N=x)	(N=x)	n (%)
	n (%)					
Decrease (an increase < 0 ms)	xx (xx.x %)	(xx.x %)				
0 ≤ Increase < 30 ms	xx (xx.x %)	xx (xx.x %)				
30 ms ≤ Increase < 60 ms	xx (xx.x %)	(xx.x %)				
Increase ≥ 60 ms	xx (xx.x %)	xx (xx.x %)				

Table 3.1.3 Summary of QTcF Actual Value by Visit

Visit	Arm 1 D0 Mean (SE) /N*	Arm 2 D400 Mean (SE) /N	Arm 3 D800-OD Mean (SE) /N	Arm 4 D1200 Mean (SE) /N	Arm 5 D800-BD Mean (SE) /N
Baseline	xx (xx.x)/N	xx (xx.x)/N	xx (xx.x) / N	xx (xx.x) / N	xx (xx.x) / N
Week 01	xx (xx.x) / N	xx (xx.x) / N	xx (xx.x) / N	xx (xx.x) / N	xx (xx.x) / N
Week 02	xx (xx.x) / N	xx (xx.x) / N	xx (xx.x) / N	xx (xx.x) / N	xx (xx.x) / N
Week 03	xx (xx.x) / N	xx (xx.x) / N	xx (xx.x)/N	xx (xx.x) / N	xx (xx.x) / N
Week 04	xx (xx.x) / N	xx (xx.x) / N	xx (xx.x) / N	xx (xx.x) / N	xx (xx.x) / N
Week 05	xx (xx.x) / N	xx (xx.x) / N	xx (xx.x) / N	xx (xx.x) / N	xx (xx.x) / N
Week 06	xx (xx.x) / N	xx (xx.x) / N	xx (xx.x) / N	xx (xx.x) / N	xx (xx.x) / N
Week 07	xx (xx.x) / N	xx (xx.x) / N	xx (xx.x) / N	xx (xx.x) / N	xx (xx.x) / N
Week 08	xx (xx.x) / N	xx (xx.x) / N	xx (xx.x) / N	xx (xx.x) / N	xx (xx.x) / N
Week 09	xx (xx.x) / N	xx (xx.x) / N	xx (xx.x) / N	xx (xx.x) / N	xx (xx.x) / N
Week 10	xx (xx.x) / N	xx (xx.x) / N	xx (xx.x) / N	xx (xx.x) / N	xx (xx.x) / N
Week 11	xx (xx.x) / N	xx (xx.x) / N	xx (xx.x) / N	xx (xx.x) / N	xx (xx.x) / N
Week 12	xx (xx.x) / N	xx (xx.x) / N	xx (xx.x) / N	xx (xx.x) / N	xx (xx.x) / N
Week 13	xx (xx.x) / N	xx (xx.x) / N	xx (xx.x) / N	xx (xx.x) / N	xx (xx.x) / N
Week 14	xx (xx.x) / N	xx (xx.x) / N	xx (xx.x) / N	xx (xx.x) / N	xx (xx.x) / N

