3.2 Safety Laboratory

Serum Chemistry

These tables will be produced for ALT, AST, Total Bilirubin, Gamma-Glutamyl Transferase, Potassium, Alkaline Phosphatase (ALP), Creatinine.

ALT

Table 3.2.1 Summary of Group Mean ALT (x ULN) Changes over time

Visit	Arm 1	Arm 2	Arm 3	Arm 4	Arm 5
	D0	D400	D800-OD	D1200	D800-BD
	Mean (SE)	Mean (SE) /N	Mean (SE) /N	Mean (SE) /N	Mean (SE) /N
	/N	5 2	ny 25	8 92	, ,
Baseline	xx (xx.x) / N				
Week 01	xx (xx.x) / N				
Week 02	xx (xx.x) / N				
Week 03	xx (xx.x) / N				
Week 04	xx (xx.x) / N				
Week 05	xx (xx.x) / N				
Week 06	xx (xx.x) / N				
Week 07	xx (xx.x) / N				
Week 08	xx (xx.x) / N				
Week 09	xx (xx.x) / N				
Week 10	xx (xx.x) / N				
Week 11	xx (xx.x) / N				
Week 12	xx (xx.x) / N				
Week 13	xx (xx.x) / N				
Week 14	xx (xx.x) / N				
Week 15	xx (xx.x) / N				
Week 16	xx (xx.x) / N				
Week 18	xx (xx.x) / N				
Week 26	xx (xx.x) / N				

Page **38** of **46**

PanACEA - DECODE - 01

v1.0, February 13, 2023

| Week 38 | xx (xx.x) / N |
|---------|---------------|---------------|---------------|---------------|---------------|
| Week 52 | xx (xx.x) / N |

Table 3.2.2 Summary of Absolute value ALT (IU/L) Changes over time

Visit	Arm 1 D0 Mean (SE) /N	Arm 2 D400 Mean (SE) /N	Arm 3 D800-OD Mean (SE) /N	Arm 4 D1200 Mean (SE) /N	Arm 5 D800-BD Mean (SE) /N
Baseline	0	0	0	0	0
Week 01	xx (xx.x) / N	xx (xx.x) / N	xx (xx.x) / N	xx (xx.x) / N	xx (xx.x) / N
Week 02	xx (xx.x) / N	xx (xx.x) / N	xx (xx.x) / N	xx (xx.x) / N	xx (xx.x) / N
Week 03	xx (xx.x) / N	xx (xx.x) / N	xx (xx.x)/N	xx (xx.x) / N	xx (xx.x) / N
Week 04	xx (xx.x) / N	xx (xx.x)/N	xx (xx.x)/N	xx (xx.x) / N	xx (xx.x) / N
Week 05	xx (xx.x) / N	xx (xx.x) / N	xx (xx.x) / N	xx (xx.x) / N	xx (xx.x) / N
Week 06	xx (xx.x) / N	xx (xx.x)/N	xx (xx.x)/N	xx (xx.x) / N	xx (xx.x) / N
Week 07	xx (xx.x) / N	xx (xx.x) / N	xx (xx.x) / N	xx (xx.x) / N	xx (xx.x) / N
Week 08	xx (xx.x) / N	xx (xx.x) / N	xx (xx.x) / N	xx (xx.x) / N	xx (xx.x) / N
Week 09	xx (xx.x) / N	xx (xx.x) / N	xx (xx.x) / N	xx (xx.x) / N	xx (xx.x) / N
Week 10	xx (xx.x) / N	xx (xx.x) / N	xx (xx.x) / N	xx (xx.x) / N	xx (xx.x) / N
Week 11	xx (xx.x) / N	xx (xx.x) / N	xx (xx.x) / N	xx (xx.x) / N	xx (xx.x) / N
Week 12	xx (xx.x) / N	xx (xx.x) / N	xx (xx.x) / N	xx (xx.x) / N	xx (xx.x) / N
Week 13	xx (xx.x) / N	xx (xx.x) / N	xx (xx.x) / N	xx (xx.x) / N	xx (xx.x) / N
Week 14	xx (xx.x) / N	xx (xx.x) / N	xx (xx.x) / N	xx (xx.x) / N	xx (xx.x) / N
Week 15	xx (xx.x) / N	xx (xx.x) / N	xx (xx.x) / N	xx (xx.x) / N	xx (xx.x) / N

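### Unscheduled tests can fill or displace values in the by-visit laboratory and ECG means, and 7 of 21 laboratory rows and 8 of 21 ECG rows have no scheduled test behind them

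*SAP*

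**What the plan says.** SAP 12.6 dates data by the actual visit and then assigns rows: "Any visit, scheduled or unscheduled, that falls into the analysis window below will be assigned to that visit for the purpose of analysis". When two visits share a window, "the one closet to the target date will be used for the analyses by visit". Nothing gives priority to the scheduled visit, and no rule covers two visits equally far from the target. The scope is stated: "These visit windows relate to analyses of tabulations of data by visit".

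That scope takes in the safety shells in the SAP appendix. "Table 3.1.3 Summary of QTcF Actual Value by Visit" and "Table 3.2.1 Summary of Group Mean ALT (x ULN) Changes over time" both print mean (SE) and N by arm for Baseline, every week from 01 to 16, and Weeks 18, 26, 38 and 52. The other ECG by-visit mean tables and all the 3.2.x laboratory mean tables reuse these layouts or their change-from-baseline versions.

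The protocol tests less often than that. Section 10.5.2 lists "Safety Lab (WK01-09, WK11, WK13, WK16): haematology and biochemistry"; section 10.5.1 adds a screening sample and section 10.5.3 adds Week 18 only. ECGs, in the Schedule of Events and section 10.5.2, are at screening and WK00, then at WK01 to 09, 11, 13 and 16.

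The protocol also generates extra tests. After a transaminase rise above three times the upper limit, section 20.1.2 calls for "Repeating liver enzyme, serum bilirubin tests and coagulation tests two or three times weekly". Section 13.10 requires ECGs every day or more often after grade 3 QTcF prolongation.

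**The concern.** A by-visit mean is read as the course of an arm over time. That reading needs roughly the same patients in each row, measured for the same planned reason. Where a row has no planned test, the patients in it are those who happened to be tested, and the reason for testing is often related to the value. A reader following ALT or QTcF from Week 9 to Week 10 would compare nearly the whole arm with a handful of selected patients.

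The trial's stated aim is to choose the dose with the best efficacy at acceptable safety (protocol 8.1), so readers will compare these profiles between arms. The trial is open-label (protocol 13.6), and the amount of extra testing could differ by dose, either because toxicity does or because clinicians know the dose. A difference between arms in such a row could then reflect who was tested rather than what the drug did.

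At weeks with a scheduled test the effect is milder: an unscheduled test nearer the target day replaces the planned one for that patient.

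**Working it through.** The plan gives no figure on this point, so the check is a count followed by two illustrations.

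**1. Rows in the shells.** Baseline (1) + Weeks 01–16 (16) + Weeks 18, 26, 38 and 52 (4) = 21.

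**2. Rows with a scheduled test.**
- Laboratory: Baseline (1) + WK01–09 (9) + WK11, 13 and 16 (3) + WK18 (1) = 14. Rows without: 21 − 14 = 7 (Weeks 10, 12, 14, 15, 26, 38 and 52).
- ECG: Baseline (1) + WK01–09 (9) + WK11, 13 and 16 (3) = 13. Rows without: 21 − 13 = 8 (the same seven plus Week 18).

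A sentence in protocol 11.3 could be taken to mean an ECG at every visit, but the opening of section 11 defers timing to the Schedule of Events, and section 10.5.2 names the weeks.

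**3. What can enter the unscheduled rows.**
- For-cause repeats: liver tests (20.1.2) and ECGs (13.10).
- Withdrawal-day tests: protocol 13.7 asks for the WK16 panel, with safety laboratory and ECG, on the day a participant leaves for any reason.
- Precautionary ECGs: with QT-prolonging drugs after treatment (12.6.5) or repeated or higher-dose metoclopramide (21.1.1).
- Late scheduled visits: a WK09 sample taken on day 67 falls in the Week 10 window (67–73); a WK11 sample on day 81 falls in Week 12 (81–87).
- Clock shift: the SAP counts from randomization, which protocol 10.5.2 allows before WK00, although the Schedule of Events shows it on Day 01. Mapping on-time tests (±2 days; WK02 −2 to 0; WK18 ±4) for an assumed gap of 0 to 8 days gives no spill at 0–1 day. At 2–8 days, Weeks 10, 12 and 14 can receive a scheduled test. At 8 days a WK16 ECG can reach Week 18 (110 to 114, plus 8, touches 122). Weeks 15, 26, 38 and 52 never receive one.

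The late windows are wide: days 155–210 for Week 26, 211–313 for Week 38, and no upper limit for Week 52. One off-schedule test in such a period can become the arm's row.

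**4. Displacement at scheduled weeks (illustration).** Assume the scheduled test falls uniformly on offsets −2 to +2 and one unscheduled test falls uniformly on the other days of the seven-day window. There are 5 × 6 = 30 pairs. The unscheduled test is strictly nearer in 8 (6 when the scheduled offset is ±2, 2 when it is ±1): 8/30 = 27%. They tie in 4/30 = 13%, for which the SAP has no rule. With daily ECGs one always falls on the target day, so the scheduled ECG is displaced for 4 of the 5 offsets, or 80%.

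**5. Size of the distortion in an unscheduled row (assumed values).** Take an arm of 15 with k patients under close liver monitoring at 5 × ULN and the rest at 0.7 × ULN. The full-arm mean is (5k + 0.7(15 − k))/15:
- k = 1: 14.8/15 = 0.99
- k = 2: 19.1/15 = 1.27
- k = 3: 23.4/15 = 1.56

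If only the monitored patients have a Week 10 test, the Week 10 row shows 5.0 × ULN with N = k in every case.

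**The case against.** These are descriptive tables with no planned test. Each cell prints N, so an odd mean would appear beside a very small count. The primary safety endpoint is a proportion of patients with graded, related events and does not draw on them. The SAP calls the shells guidance that may be updated, so 21 identical rows look like a generic template. Extreme values have other outlets: SAP 13.1.1 tabulates each patient's highest QT and QTcF after randomization, SAP 13.2 promises to describe patients who worsen from baseline, and clinically significant laboratory changes become adverse events under protocol 14.10. All of this stands and limits the harm. It does not make the rows comparable: N warns the reader but does not correct the mean, and the laboratory parameters have no worst-value or shift shell, so by-visit means are the only laboratory display laid out.

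A reader might infer that the unscheduled rows contain only patients tested because something was wrong. The documents do not support that, since withdrawal-day panels, precautionary ECGs and late or clock-shifted scheduled tests can enter too. A reader might also infer that repeat tests are pooled, so that a closely monitored patient counts several times. SAP 12.6 rules this out by keeping one visit per patient per row; an unscheduled test fills an empty cell or displaces the scheduled value.

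**Conclusion.** The concern holds as a selection problem in descriptive safety displays. Followed as written, the SAP gives arm means in 7 of 21 laboratory rows and 8 of 21 ECG rows that have no protocol-scheduled test, and those means cannot be compared across weeks or dose arms. The counts rest only on the protocol's schedule and the SAP shells. At scheduled weeks, displacement is possible and its frequency depends on testing patterns; the 27% and 80% figures, like the ALT example, rest on the stated assumptions and only illustrate scale. How many tests will land in the unscheduled rows, and in which arms, cannot be known from the documents.

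It would go too far to say that the primary safety endpoint is biased or that a QTcF signal would be lost: neither depends on these means. The change is worth making because it is cheap and these profiles will be read when doses are compared.

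**What to change.** For laboratory and ECG by-visit summaries only:

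- Use the protocol-scheduled assessment, assigned to its nominal visit, and leave the cell missing if it was not done. Delete Weeks 10, 12, 14, 15, 26, 38 and 52 from the laboratory tables, and those weeks plus Week 18 from the ECG tables.
- Apply this to Tables 3.1.3 and 3.1.4, to the ECG tables that reuse those two shells (3.1.7, 3.1.8, 3.1.11, 3.1.12, 3.1.15, 3.1.16, 3.1.19, 3.1.20, 3.1.23 and 3.1.24), and to the 3.2.x mean tables. The ECG tables built on the categorical shells 3.1.1 and 3.1.2 are not affected.
- Leave the SAP 12.6 windows unchanged for sputum culture, conversion and relapse, where unscheduled samples at suspected recurrence must still count.
- Keep every result, including unscheduled ones, in worst-post-baseline summaries. Retain the highest-value QT and QTcF tables in SAP 13.1.1, with any QTcF grading by protocol Table 2, which replaces CTCAE for that measure. Add a worst post-baseline CTCAE grade or shift table by arm for the laboratory parameters.

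The cost is SAP wording and table programming, with fewer rows in the by-visit tables. No new data are needed, and when patients are tested does not change.

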13.1. Safety Variables

13.1.1. ECG Analysis

QT and QTcF (Friderica's correction) data will be analyzed categorically based on the number and percentage of participants classified in each category by treatment group, in addition to summarizing mean QT/QTcF over time by dose group.

Post-baseline QT and QTcF intervals will be classified into following categories:

- QT/QTcF < 450 ms
- 450 ms <QT/QTcF <480 ms
- 480 ms < QT/QTcF < 500 ms
- QT/QTcF > 500 ms

QTcF changes from baseline will be classified into the following categories:

- Decrease (an increase < 0 ms)
- Increase < 30 ms
- >30 ms and < 60 ms
- increase >60 ms

QT and QTcF will be categorized ($<450, 450-479, 480-499, \ge 500$) and tabulated by visit and treatment arm, and highest post-randomization value overall by treatment arm. Change from baseline of QT and QTcF will also be categorized ($<30, 30-59, \ge 60$) and tabulated by treatment arm, and highest post-randomization value overall by treatment arm. These tables will be done for the whole study period and repeated for the treatment phase only.

Frequency, severity and type of ECG alterations will be tabulated and described.

Both mean (and SE) QT, QTcF, PR, RR, QRS, and heart rate (HR) by visit and treatment arm, and mean (and SE) QT, QTcF, PR, RR, QRS, and HR change from baseline by visit (within visit window) and treatment arm will be tabulated.

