  - c. Serious lung conditions other than TB, or significant respiratory impairment in the discretion of the investigator
  - d. Any diabetes mellitus
  - e. Cardiovascular disease such as myocardial infarction, heart failure, coronary heart disease, arrhythmia, tachyarrhythmia, or pulmonary hypertension
  - f. Arterial hypertension (systolic blood pressure ≥140 mmHg and/or diastolic blood pressure of ≥90 mmHg on two occasions during screening).
  - g. Long QT syndrome or family history of long QT syndrome or family history of sudden death of unknown or cardiac-related cause
  - h. Alcohol or other drug abuse that is sufficient to significantly compromise the safety or cooperation of the patient, that includes substances prohibited by the protocol or has led to significant organ damage at the discretion of the investigator.
- 8. Any of the following laboratory findings at screening:
  - a. Serum amino aspartate transferase (AST) and/or alanine aminotransferase (ALT) >3x the upper limit of normal (ULN),
  - b. Serum alkaline phosphatase or y-glutamyl transferase > 2.5x the ULN,
  - c. Serum total bilirubin level >1.5x the ULN
  - d. Estimated creatinine clearance (eCrCl; using the Cockroft and Gault formula [57] lower than 30 ml/min
  - e. Serum albumin < 2.8 g/dl
  - f. Haemoglobin level <7.0 g/dl
  - g. Platelet count <50,000/mm^3,

- h. Serum potassium below the lower level of normal for the laboratory
- i. Blood glucose at screening of less than 70mg/dL (3.9mmol/L)
- 9. ECG findings in the screening ECG: (one or more):
  - a. QTcF of >0.450 s
  - b. Atrioventricular (AV) block with PR interval > 0.20 s,
  - c. QRS complex > 120 milliseconds
  - d. Any other changes in the ECG that are clinically relevant as per discretion of the investigator
- 10. Restricted medication:
  - a. Treatment with any other investigational drug within 1 month prior to enrolment or enrolment into other clinical (intervention) trials during participation.
  - b. Previous anti-TB treatment with drugs active against MTB within the last 3 months prior to screening.
  - c. Unable or unwilling to abide by the requirements regarding restricted medication or have taken restricted medication as described under section 12.6, page 59.
     Restricted medication includes the following drug classes:
    - Anti-TB drugs other than study drugs
    - Medication that lowers the threshold for epileptic seizures
    - Medication that prolongs the QTc interval

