#### Table 2: definition of severity grading of QTcF prolongation

This deviation from the CTCAE severity grading is necessary due to the specific situation of TB patients; a population in whom a change in QTc over baseline is difficult to assess. Before

treatment starts, they are sick, have elevated temperature and are distressed by their first contact with the trial team, which influences the QT interval, through elevated heart rate and possibly other mechanisms.

In a specific analysis of the Oflotub phase III study, it was confirmed that the elevated heart rates at baseline were associated with lower QTcF; and that specifically at baseline, QTcF correction undercorrects at these high heart rates of TB patients [76].

Further, QTc at baseline and late during treatment were compared. A mean increase in QTcF of 11.2 ms was found in the Gatifloxacin arm, and 9.8 ms in the control arm; despite the fact that for none of the drugs, a correlation between Cmax and QTc prolongation could be described.

Due to this limitation, there is a risk that an incorrect signal of QTcF prolongation over baseline in a patient will occur that in itself will not show a safety hazard to the patient, but will result in lifesaving drugs being withheld. Therefore, assessment of severity of QTcF prolongation and the stopping of treatment in this study as laid out in *Table 2: definition of severity grading of QTcF prolongation*, follows the precedent of the ACTG A5343 trial mentioned above; where a combination of bedaquiline and delamanid was trialled and assessed for its potential to prolong the QT interval [77].

Here, in order to prevent a false signal that might be due to a change in heart rate between assessments, a higher grade QTcF prolongation is defined as a combination of QTcF prolongation from baseline with an elevated absolute value, not a prolongation alone.

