#### 15.3.1 ECG analysis

QT and QTc data will be analysed categorically based on the number and percentage of patients classified in each category by treatment group. QTc data will be presented for Friderica's corrections.

Post-baseline QT- and QTc-intervals will be classified into the following categories:

- QT/QTc<450 ms
- 450 ms <QT/QTc <480 ms
- 480 ms < QT/QTc < 500 ms
- QT/QTc > 500 ms

QTc-changes from baseline will be classified into the following categories:

- decrease (an increase < 0 ms)
- increase < 30 ms
- >30 ms and < 60 ms
- increase >60 ms

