Table 3.1.16 Summary of RR Changes from Baseline Value by Treatment Arm

{Similar shell table as Table 3.1.4}

ORS

Table 3.1.17 Summary of QRS Actual Value by Visit

{Similar shell table as Table 3.1.1}

Table 3.1.18 Participants Proportion of QRS Changes from Baseline by Treatment Arm

{Similar shell table as Table 3.1.2}

Table 3.1.19 Summary of QRS Actual Value by Visit

{Similar shell table as Table 3.1.3}

Table 3.1.20 Summary of QRS Changes from Baseline Value by Treatment Arm

{Similar shell table as Table 3.1.4}

Page 37 of 46

Heart Rate (HR)

Table 3.1.21 Summary of HR Actual Value by Visit

{Similar shell table as Table 3.1.1}

Table 3.1.22 Participants Proportion of HR Changes from Baseline by Treatment Arm

{Similar shell table as Table 3.1.2}

Table 3.1.23 Summary of HR Actual Value by Visit

{Similar shell table as Table 3.1.3}

Table 3.1.24 Summary of HR Changes from Baseline Value by Treatment Arm

{Similar shell table as Table 3.1.4}

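### The SAP categorises uncorrected QT change with QTcF cut points, and its shells carry the QTcF bands to PR, RR, QRS and heart rate, where the absolute bands say almost nothing

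*SAP*

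**What the plan says.** SAP 13.1.1 sets out change-from-baseline categories twice. The first list covers QTcF alone: "QTcF changes from baseline will be classified into the following categories". That matches protocol 15.3.1: "QTc-changes from baseline will be classified into the following categories". The SAP then adds "Change from baseline of QT and QTcF will also be categorized", with three levels (<30, 30-59, ≥60 ms), by arm and for the highest post-randomisation value. Absolute bands for both QT and QTc are in the protocol as well as the SAP.

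The SAP appendix, section 3.1 ECG, opens with "These tables will be produced for QTcF,QT, PR, RR, QRS", and heart rate is added further down. Table 3.1.1 holds the absolute bands (for example "450 ms ≤ QTcF <480 ms"). Table 3.1.2 holds four change bands (<0, 0 to <30, 30 to <60, ≥60 ms). The tables for PR (3.1.9, 3.1.10), RR (3.1.13, 3.1.14), QRS (3.1.17, 3.1.18) and heart rate (3.1.21, 3.1.22) are described as similar to these two; one is "Table 3.1.18 Participants Proportion of QRS Changes from Baseline by Treatment Arm". No cut points specific to PR, RR, QRS or heart rate appear anywhere.

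SAP 13.1.1 also plans mean (SE) values and mean changes by visit and arm for all these parameters, and a tabulation of ECG alterations by frequency, severity and type.

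**The concern.** Changes in PR, RR, QRS, QT and QTcF are named secondary safety endpoints, in a regimen in which three of the drugs can prolong QT. Two things look wrong.

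First, uncorrected QT depends on heart rate. Protocol 14.6 explains that patients arrive ill and distressed with raised rates, and reports from an earlier trial that "elevated heart rates at baseline were associated with lower QTcF". Its QTcF grading is built to avoid a false signal from a change in heart rate. A categorical table of uncorrected QT change brings that signal back.

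Second, QTcF cut points do not fit the other parameters. Heart rate is not measured in milliseconds. PR and QRS are far shorter than 450 ms, and exclusion criterion 9 removes patients with PR above 0.20 s or "QRS complex > 120 milliseconds".

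**Working it through.** The documents state no figure for these tables, so there is none to reproduce.

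**Absolute bands for PR, RR, QRS and heart rate**

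- PR: from the 200 ms entry limit, 450 − 200 = 250 ms of lengthening is needed to leave the lowest band.
- QRS: from the 120 ms entry limit, 450 − 120 = 330 ms is needed.
- RR = 60000/HR, so RR < 500 ms needs HR > 60000/500 = 120 bpm.
- Every heart rate in bpm is below 450.

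**Change bands for PR and QRS.** These do respond. A PR of 280 ms is a rise of at least 280 − 200 = 80 ms for a patient within the entry limit, so it counts as ≥60 ms in Table 3.1.10. A QRS of 160 ms is a rise of at least 160 − 120 = 40 ms, so it counts as 30 to <60 ms or higher in Table 3.1.18. A smaller crossing is missed: PR going from 190 to 215 ms passes the 200 ms limit but is a change of 25 ms (0 to <30) and an absolute value <450.

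**Mean tables.** With 15 per arm and assumed SDs of change of 15 ms (PR) and 8 ms (QRS), the standard errors are 15/√15 = 3.9 ms and 8/√15 = 2.1 ms. Between-arm differences of 20 ms (PR) and 10 ms (QRS) would have power of about 0.95 and 0.93. A single outlier is diluted: PR going from 180 to 280 ms moves the arm mean by 100/15 = 6.7 ms.

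**Uncorrected QT change.** QT = QTcF × (60/HR)^(1/3). With QTcF fixed at 400 ms:

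- HR 100 to 75 bpm: 371.3 − 337.4 = +34 ms.
- HR 110 to 75 bpm: 371.3 − 326.8 = +44.5 ms.

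The SAP takes the highest value. The schedule gives 12 on-treatment ECGs (weeks 1-9, 11, 13, 16) after a triplicate baseline. Simulation with no drug effect assumed mean QTcF 410 ms, between-patient SD 15 ms, within-patient SDs of 10 ms for QTcF and 8 bpm for heart rate, and perfect Fridericia correction. The documents give none of these values.

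| Heart rate, baseline to on treatment | Highest QT change ≥30 ms |
|---|---|
| 90 to 90 bpm | 29% |
| 90 to 80 bpm | 81% |
| 95 to 80 bpm | 92% |
| 100 to 80 bpm | 98% |

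Highest QTcF change ≥30 ms occurs in 5% throughout. Modelling baseline heart rate differently gives 77-83%, 88-94% and 95-98% for the three falls. Smaller within-patient SDs (7 ms, 5 bpm) with a 15 bpm fall still give about 80%.

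**Response to a drug effect.** In the 95 to 80 bpm case, adding the 20.7 ms QTcF effect that protocol 7.4 quotes for bedaquiline with delamanid raises the share with QT change ≥60 ms from 17% to 71%.

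**The case against.** The case against is strong on how much harm follows, and most of it stands.

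- A reader might infer that a real conduction change would go unseen. It would not: mean tables for PR and QRS, the four-level change shells and the tabulation of ECG alterations are all planned.
- A reader might infer that nearly every patient falls in one category whatever the drug does. That is right for the absolute PR, RR, QRS and heart-rate bands. It is wrong for the QT-change table, which spreads patients and moves with a drug effect.
- A reader might infer a false delpazolid signal. All arms receive the same three background drugs, and a heart-rate fall common to all arms raises every arm alike. It does not by itself create a dose difference. The documents give no data on whether heart-rate recovery differs by arm.
- The 5% figure for QTcF flatters QTcF. Protocol 14.6 says Fridericia correction undercorrects at these high rates and reports mean QTcF rises of 11.2 and 9.8 ms in the two arms of an earlier trial. A 10 ms drift takes the 5% to 31%, so the contrast narrows but remains.
- The carry-over to PR, RR, QRS and heart rate looks clerical. The SAP text sets no categories for them. Tables 3.1.9, 3.1.13, 3.1.17 and 3.1.21 have titles that do not match Table 3.1.1, and the appendix calls the shells guidance that may be updated. This makes correction easy but does not supply the missing cut points.
- Removing the absolute bands for uncorrected QT would depart from protocol 15.3.1, so those bands should stay.

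**Conclusion.** The point holds as a minor fault in descriptive secondary safety tables. The SAP extends change categories to uncorrected QT beyond its own list and the protocol. In patients whose heart rate falls on treatment, that table would show apparent prolongation in many patients in every arm without any drug effect. Its size rests on assumed heart-rate falls and variability: about 30% at ≥30 ms with no fall, about 80-98% with falls of 10-20 bpm. The direction follows from the Fridericia formula alone.

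The absolute QTcF bands, read across to PR, RR, QRS and heart rate, carry almost no information. What is lost is the absolute outlier view of PR and QRS. The primary endpoints, the QTcF tables and the QTcF secondary endpoints (>500 ms; grade 3 and above) are unaffected.

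**What to change.** - In SAP 13.1.1, limit the change-from-baseline categories to QTcF. Show uncorrected QT change only in the mean (SE) tables already planned, and delete shell 3.1.6.
- Keep the absolute bands for QT and QTcF, as protocol 15.3.1 requires.
- For PR and QRS, replace shells 3.1.9, 3.1.10, 3.1.17 and 3.1.18 with counts by arm of new on-treatment exceedances of the exclusion criterion 9 limits (PR >200 ms, QRS >120 ms): within the limit at baseline and above it on treatment. These are reporting thresholds only and imply nothing about patient management.
- Delete the categorical shells for RR (3.1.13, 3.1.14) and heart rate (3.1.21, 3.1.22). Their mean tables remain.

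The cost is one sentence in 13.1.1 and nine shells (1 + 4 + 4), with no new data and no departure from the protocol's ECG categories. The uncorrected-QT change category table is lost; it is hard to interpret without heart rate.
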